6.2. Exclusion Criteria

Subjects meeting any of the following exclusion criteria are not to be enrolled in the study to treatment:

1. Prior treatment with a KIT inhibitor for melanoma
2. Known presence of NRAS or BRAF mutation
3. Exposure to any chemotherapy, antibody or antibody drug conjugate, small molecule TKI, immunotherapy (e.g., PD-1, PD-L1, or CTLA-4 inhibitors – either antibody or small molecule), investigational drug, or radiation therapy within 28 days prior to Cycle 1 Day 1 (C1D1).
4. Unresolved Grade >1 clinically significant (in the judgment of the investigator) adverse effects from previous therapy prior to C1D1
5. Symptomatic brain metastases. Subjects with untreated brain metastasis ≤ 1 cm can be considered eligible if deemed asymptomatic by the investigator upon consultation with the medical monitor and do not require immediate radiation or steroids. Subjects with brain metastasis that is treated and stable for 1 month may be considered eligible if they are asymptomatic and on stable dose of steroids or if they do not require steroids following successful local therapy.
6. History of another malignancy (within 2 years prior to first study drug administration) unless malignancy was treated with curative intent and likelihood of relapse is small (<5% in 2 years in the judgment of the investigator). Patients with a history of squamous or basal cell carcinoma of the skin or carcinoma in situ of the cervix may be enrolled.
7. Concomitant treatment with other anti-neoplastic agents (hormonal therapy acceptable)
8. Uncontrolled intercurrent or infectious illness
9. Major surgical procedure or significant traumatic injury within 14 days of initiating study drug or anticipation of the need for major surgery during the study
10. Previous radiotherapy to 25% or more of the bone marrow and/or radiation therapy within 28 days prior to C1D1
11. Inability to swallow capsules, or refractory nausea and vomiting, malabsorption, an external biliary shunt, or significant bowel resection that would preclude adequate absorption
12. Congestive heart failure (CHF) New York (NY) Heart Association class III or IV; unstable coronary artery disease (myocardial infarction [MI] more than 6 months prior to study entry is permitted); or serious cardiac arrhythmia
13. Baseline QTcF ≥ 450 ms (males) or ≥ 470 ms (females)

14. Known active or chronic infection with human immunodeficiency virus (HIV), hepatitis C virus (HCV), or hepatitis B virus (HBV). Active or chronic HBV infection is defined as being hepatitis B surface antigen (HBsAg) or HBV DNA-positive. Chronic HCV is defined as being anti-HCV or HCV RNA-positive
15. Known chronic liver disease
16. Women who are breast-feeding or pregnant

7.0 STUDY TREATMENT

7.1 Study Drug Administration

PLX3397 will be supplied in 200 mg capsules and will be taken BID approximately 12 hours apart. Each dose is to be taken with approximately 200 mL of water. Subject will fast for at least one hour before and one hour after dosage. Each cycle of treatment will last 28 days.

The dose level for the Phase II portion of the study will be the RP2D as determined from the Pilot phase. Study drug will be administered BID in a fasting state for at least one hour before and one hour after administration.

Missed doses (generally outside of a 2-hour dosing window) will be skipped and not administered as a double dose at the next administration. Patients who omit their dose will be instructed NOT to make up that dose. Doses that are vomited will not be replaced.

7.2 Dose Levels for Pilot Portion of the Study

7.2.1 Dose Evaluation

During the Pilot portion of the study, 3 to 6 patients in sequential dose cohorts will be enrolled. The dose cohorts are as follows:

- Cohort 1: 1000 mg/day (400 mg in the morning and 600 mg in the evening)
- Cohort -1(if required): 800 mg/day (400 mg BID)

Cohort -1 will be carried out only if Cohort 1 is considered intolerable. Study treatment may be delayed up to 2 weeks to permit resolution of any treatment-related toxicity outside the DLT window.

7.3 Dose Reduction Rules

Dose reduction will occur in accordance with the rules listed below.

- The DLT window is 28 days.

- A minimum of 3 patients will be initially enrolled per cohort.
- If 0 or 1 of the first 3 patients enrolled in a given cohort experiences a DLT, at least 3 additional patients will be enrolled in that cohort.
- If a DLT is observed in one-third or more of patients (e.g., 2 or more of up to 6 patients), the dose combination at which this occurs will be considered intolerable and the maximum tolerated dose (MTD) will have been exceeded and the next lower dose will be evaluated.
- The highest dose level at which 0 or 1 out of 6 experiences a DLT will be declared the MTD. If only 3 patients were initially evaluated at that dose level, an additional 3 patients will be enrolled to evaluate for DLTs at that dose level.
- After dosing has been completed in each cohort, safety and PK data (as applicable) will be reviewed by and dose reduction decisions made by the Sponsor, and investigators and study staff from all participating sites.

7.4. Definitions of Dose-Limiting Toxicity

In the Pilot portion of the study, DLTs will be assessed during a DLT assessment window of 28 days in Cycle 1. However, if clinically relevant \geq Grade 3 cumulative toxicities are observed beyond Cycle 1, these should also be taken into account when assessing further dose reduction.

There will be a 24 hour delay between the first and subsequent patients enrolled in each cohort to maximize the safety of enrolled patients.

Patients who are withdrawn from the study prior to completing the DLT assessment window for any reason other than a DLT will be replaced. Patient numbers must not be re-used.

Subjects who receive less than 80% of the planned dose during the DLT evaluation period will not be considered evaluable and need to be replaced.

A DLT is defined as an AE assessed as being possibly or probably related to study drug administration that is:

- Not due to the underlying malignancy;
- Has no clear evidence of an alternative etiology; and
- Meets one of the following CTCAE v. 4.03 criteria during the first 28 days of PLX3397 administration:
 - Any Grade \geq 3 clinically significant hematologic toxicity except:
 - Grade 3 lymphopenia
 - Grade 3 neutropenia \leq 7 days
 - Any thrombocytopenia resulting in clinically significant bleeding
 - Any Grade \geq 3 clinically significant non-hematologic toxicity except:

- Nausea, vomiting, and/or diarrhea of Grade 3 severity that resolves to Grade ≤ 2 within 7 days with optimal prophylaxis and/or treatment.
- Grade 3 fatigue that resolves to Grade ≤ 2 within 7 days.
- Grade ≥ 3 alkaline phosphatase that is related to underlying malignancy (e.g., bone metastasis)
- If, for any reason, either the Sponsor or principal investigator deems further dose reduction inappropriate. Final decisions on determination of DLTs will be made in consultation between the Sponsor and the principal investigator.
- Any dose reduction required during Cycle 1 due to potential toxicity.
- For the purposes of determining the DLT in Cycle 1, the use of G-CSF or other hematologic growth factors is not permitted during Cycle 1. If a patient develops a protocol defined hematologic DLT and requires the use of G-CSF or other hematologic growth factors, they may be used in accordance with local standard of care, and per Section 7.7.

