7.5. Dose-Modification Guidelines

Toxicities that occur outside the DLT window will be taken into consideration when determining the RP2D. Reduction/interruption of dosing for AEs may take place at any time. Below are guidelines for dosage modification for PLX3397–related toxicities as well as guidelines for their management. Dose reductions should occur in increments of 200 mg/day, depending on the toxicity grade, as noted in [Table 7-1](#) and [Table 7-2](#).

These parameters are only a guide and are not intended to supersede the clinical judgment of the treating physician. Medical Monitor should be notified of any dose adjustments. Dosing interruptions longer than 2 weeks for any reason should generally result in discontinuation from the study, unless the patient has demonstrated a clinical benefit from therapy and would like to continue dosing with study drug after discussion between the investigator and the Sponsor. Rechallenge with a reduced dose of pexidartinib may result in a recurrence of increased serum transaminases, bilirubin, or ALP. Monitor liver tests weekly for the first month after rechallenge.

Table 7-1: Dose Modification Guidelines for Treatment-emergent Toxicities

Adverse Reaction	Severity	Pexidartinib Dosage Modifications
Increased ALT and/or AST	Greater than 3 to 5 times ULN	
 • Withhold and monitor liver tests weekly. • If AST and ALT are less than or equal to 3 times ULN within 4 weeks, resume at reduced dose. • If AST or ALT is not less than or equal to 3 times ULN in 4 weeks, permanently discontinue pexidartinib.

	Greater than 5 to 10 times ULN	
 Withhold and monitor liver tests twice weekly. If AST and ALT are less than or equal to 3 times ULN within 4 weeks, resume at reduced dose. If AST or ALT is not less than or equal to 3 times ULN in 4 weeks, permanently discontinue pexidartinib.
	Greater than 10 times ULN	
 Permanently discontinue pexidartinib. Monitor liver tests twice weekly until AST or ALT is less than or equal to 5 times ULN, then weekly until less than or equal to 3 times ULN.
Increased ALP and Gamma-glutamyl transpeptidase (GGT)	ALP greater than 2 times ULN with GGT greater than 2 times ULN	
 Permanently discontinue pexidartinib. Monitor liver tests twice weekly until ALP is less than or equal to 5 times ULN, then weekly until less than or equal to 2 times ULN.

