7.6. Stopping Rules

Following are the stopping rules for the Pilot portion of the study:

- If ≥ 2 of 6 patients experience DLTs in cohort 1 (1000 mg/day), Cohort -1 (800 mg per day) will be activated.
- If ≥ 2 of 6 patients in Cohort -1 experience DLTs, the study will be terminated due to intolerability.

Following are the stopping rules for the Phase II portion of the study:

- Subjects will be discontinued from the study for reasons of AE, clinically significant disease progression, patient request, investigator decision, protocol violation, patient noncompliance, and study termination by the Sponsor or institutional review board (IRB)/independent ethics committee (IEC). See Section 7.5 for guidance on dose reduction and discontinuation of therapy for safety concerns. Noncompliant patients may be replaced.

Patients will be discontinued from the study if they are off study drug for more than 2 weeks, regardless of the reason, unless the patient has demonstrated a clinical benefit from therapy and

would like to continue dosing with study drug after discussion between the investigator and the Sponsor.

The Pilot and Phase II portions of the study may be discontinued if the study is terminated by the Sponsor, the China Food and Drug Administration (CFDA), or other regulatory authorities.

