8.4. Withdrawal of Patients from Drug Treatment, Study and Patient Replacement

The Medical Monitor will monitor safety data throughout the course of the study. The Medical Monitor will review SAEs within timeframes mandated by company procedures and will review trends, laboratory data, and AEs at periodic intervals and provide for interim safety analyses if appropriate.

The reasons a patient may discontinue or be withdrawn from the study include, but are not limited to, AE, clinically significant disease progression, patient request, investigator decision,

protocol violation, patient noncompliance, and study termination by the Sponsor or IRB/IEC. When a patient discontinues or is withdrawn, the investigator will notify the Sponsor and should perform the procedures indicated in the End of Study column in the Schedule of Events within 28 days after discontinuation of study drug and before initiation of any new anti-cancer therapy. Follow-up information will be obtained for patients who discontinue their participation in or are withdrawn from the study.

Patients withdrawn from the study for reasons other than toxicity or clinically significant disease progression (e.g., protocol violation or noncompliance) may be replaced at the discretion of the medical monitor and the investigator. Study drug administration may be discontinued due to an AE or at the discretion of the investigator.

The consequence of withdrawal of consent by a patient will be that no new information will be collected from that patient and added to the existing data or any database. However, every effort will be made to follow all patients for safety.

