10.0 STUDY ENDPOINTS

10.1. Pilot Portion

The endpoints in the Pilot portion of the study include:

- DLTs will define the RP2D (1000 mg per day or 800 mg per day)
- Safety endpoints (i.e., AEs, clinical laboratory evaluations, ECGs, physical examinations, and vital sign measurements)
- Pharmacokinetic (PK) analysis
- Serum/plasma tumor biomarkers including CSF-1

The exploratory endpoints in the Pilot portion of the study include:

- Immunohistochemistry (IHC) and molecular analysis of archival and paired fresh tumor biopsy
- PET scan evaluation on Day 1 of Cycle 2 compared to Baseline

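### The 80%-of-dose replacement rule in Section 7.4 has no DLT exception, so read literally it can remove DLT cases from the pilot DLT count

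*Combined protocol and SAP*

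**What the plan says.** Section 7.4 of the protocol contains two replacement rules for the 28-day DLT window.

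- Withdrawals: "Patients who are withdrawn from the study prior to completing the DLT assessment window for any reason other than a DLT will be replaced". By implication, a patient withdrawn because of a DLT is kept.
- Dose received: "Subjects who receive less than 80% of the planned dose during the DLT evaluation period will not be considered evaluable and need to be replaced". No cause is named and no exception is made.

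The list of DLT criteria in the same section includes "Any dose reduction required during Cycle 1 due to potential toxicity".

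Section 8.4 allows discretionary replacement for "Patients withdrawn from the study for reasons other than toxicity or clinically significant disease progression". Like the first rule in 7.4, it covers withdrawals only.

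In Section 7.5, Table 7-1 pairs holds with restarts at a lower dose. For ALT/AST elevations, for example: "If AST and ALT are less than or equal to 3 times ULN within 4 weeks, resume at reduced dose". It also requires permanent discontinuation for some findings.

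Sections 7.3, 7.6 and 11.1 and the synopsis decide tolerability by counting patients with DLTs, two or more of six being intolerable. Section 10.1 makes DLTs the pilot endpoint that defines the RP2D. Section 11.3 defines a safety and an efficacy population but no DLT-evaluable set.

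**The concern.** A patient who has a DLT is often held, reduced or stopped because of it, and so receives less drug. Evaluability that depends on dose received, with no DLT exception, can therefore select against the events the pilot is meant to count. Two situations arise.

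- **Withdrawn for a DLT with less than 80% of dose received.** The withdrawal rule implies that the patient is kept, and the dose rule requires replacement. The two rules conflict, though only by implication, because the first never says outright that DLT withdrawals are kept.
- **DLT, dose held, patient stays on study, less than 80% received.** The withdrawal rule and Section 8.4 do not apply. Only the dose rule does, and read literally it removes the patient.

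The error can only lower the counted DLT rate and favour clearing the dose. At stake is the pilot DLT endpoint and, had the study continued, the choice of RP2D.

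**Working it through.** The plan gives no operating characteristics for the 3+3 pilot, so there is no stated figure to reproduce.

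**Inputs.** The DLT window is 28 days (7.3). Cohort 1 receives 1000 mg/day (7.2.1). Dose reductions are in 200 mg/day steps (7.5). Two or more DLTs in up to six patients is intolerable, and 0 or 1 of 6 is acceptable (7.3). The protocol does not define planned dose; I take it as 28 × 1000 = 28,000 mg. Then 80% is 22,400 mg, or 22.4 full-dose days.

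**Step 1: which DLT patients fall below 80% in Cohort 1?**

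- Permanent stop: after 22 days, 22/28 = 78.6% (below); after 23 days, 23/28 = 82.1% (not below).
- Hold without a reduction: 6 days lost gives 22/28 = 78.6%; 5 days lost gives 23/28 = 82.1%. A hold that starts after day 23 and runs past day 28 loses only 5 days in the window, so it is not below.
- Reduction to 800 mg/day without a hold: 80.0% if from day 1 and higher if later. Never below.
- Hold of h days after d full-dose days, then 800 mg/day: 1000d + 800(28 − d − h) < 22,400 reduces to 200d < 800h, that is, h > d/4.

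| Full-dose days before hold | Longest hold not below 80% | Shortest hold below 80% |
|---|---|---|
| 7 | 1 day: 82.1% | 2 days: 79.3% |
| 14 | 3 days: 81.4% | 4 days: 78.6% |
| 21 | 5 days: 80.7% | 6 days: 77.9% |

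In the last pattern the reduction is itself a DLT if it was required in Cycle 1 for potential toxicity. So some DLT patients fall below the line and others do not.

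**Step 2: effect on six patients without replacement.** One excluded DLT case turns 2/6 = 33% into 1/5 = 20%, or 1/6 = 17% into 0/5. The first change crosses the one-third threshold.

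**Step 3: the rule as designed, with replacement.** Let p be the true DLT rate and f the share of DLT patients who fall below 80% and are replaced. The documents give neither, so both are assumptions. I also assume that every patient without a DLT is evaluable. The DLT rate among evaluable patients is then q = p(1 − f)/(1 − pf), and P(dose cleared) = P(Bin(6, q) ≤ 1) = (1 − q)^6 + 6q(1 − q)^5. Stopping early at two DLTs in the first three does not change this.

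Example: p = 1/3 and f = 0.5 give q = (1/6)/(5/6) = 0.20, and P = 0.8^6 + 6 × 0.2 × 0.8^5 = 0.262 + 0.393 = 0.655.

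| Assumed p | f = 0 | f = 0.25 | f = 0.50 |
|---|---|---|---|
| 0.25 | 0.534 | 0.655 | 0.793 |
| 1/3 | 0.351 | 0.481 | 0.655 |
| 0.40 | 0.233 | 0.351 | 0.534 |

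A simulation of the sequential 3+3 (200,000 runs) at p = 1/3 gave 0.353, 0.481 and 0.657.

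**The case against.** The strongest reply is that the rule was meant for non-compliance. The synopsis, under the Phase II stopping rules, equates taking less than 80% of drug with noncompliance. The version 6.0 summary of changes, where the rule entered, gives non-compliance as its reason. Section 8.4 keeps toxicity withdrawals out of discretionary replacement. This is probably the intent, and it makes the correction uncontroversial. But none of these places puts an exception into the sentence that governs the pilot.

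Second, the decision rules count patients who experience a DLT and do not say evaluable, so a DLT might be counted anyway. That reading is possible. However, if the patient is both counted and replaced, seven patients would feed a rule written for six, and the plan does not say how to handle that.

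Third, the sponsor and investigators adjudicate DLTs, review each cohort and discuss the RP2D, so the decision is not mechanical. This stands: the probabilities in Step 3 show the direction of the written rule and do not predict what people would have decided.

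Fourth, planned dose might mean the dose scheduled up to a protocol-directed stop. On that reading such a stop creates no shortfall and the 22-day limit disappears. The range therefore runs from no DLT patient removed on that ground to all those below the limits in Step 1.

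Fifth, Table 7-1 is version 9.0 text from January 2020, while the six patients were enrolled by 30 June 2018. The hold-and-reduce patterns therefore show how the current wording works, not what happened to those patients.

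Finally, Section 5.1 records that the sponsor decided to discontinue the study after assessing six patients at 1000 mg/day. No RP2D decision remains, and the Section 11.9 AE and SAE tables still show every event. This is why the point is minor.

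**Conclusion.** The concern holds and is minor. As written, the 80% sentence conflicts by implication with the withdrawal rule in the same section and can remove from the DLT count patients whose DLT caused the dose shortfall. The direction is certain: a lower counted DLT rate. The size is not known, because the documents give no DLT count and no dose received for the six patients, and do not say which protocol version applied to each.

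For the pilot as enrolled, a single exclusion could move the result from 33% to 20%. For the rule as designed, at an assumed true DLT rate of 1/3, the chance of clearing the dose rises from 35% to 48% if a quarter of DLT patients are replaced, and to 66% if half are. These figures rest on the assumed rates and shares, and the day limits rest on a planned dose of 28 × 1000 mg. Nothing shows that any of the six was affected. What remains open is how their DLT endpoint is counted and reported.

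**What to change.** - Reconcile Sections 7.4 and 8.4 so that any patient with a DLT is evaluable and counted whatever dose was received, and the 80% replacement rule applies only to patients without a DLT. State what planned dose means.
- Enter the same definition in Section 11.3 as the DLT-evaluable set.
- In the report, give the DLT count among all six treated pilot patients and say whether anyone was excluded or replaced under the 80% rule.

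With enrolment ended, the reporting statement is the part with immediate effect. The cost is wording in three sections, one reporting sentence and a check of six Cycle 1 dosing records. No extra patients or procedures are needed. The change concerns who is counted and alters no dose or clinical rule.

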7.5. Dose-Modification Guidelines

Toxicities that occur outside the DLT window will be taken into consideration when determining the RP2D. Reduction/interruption of dosing for AEs may take place at any time. Below are guidelines for dosage modification for PLX3397–related toxicities as well as guidelines for their management. Dose reductions should occur in increments of 200 mg/day, depending on the toxicity grade, as noted in [Table 7-1](#) and [Table 7-2](#).

These parameters are only a guide and are not intended to supersede the clinical judgment of the treating physician. Medical Monitor should be notified of any dose adjustments. Dosing interruptions longer than 2 weeks for any reason should generally result in discontinuation from the study, unless the patient has demonstrated a clinical benefit from therapy and would like to continue dosing with study drug after discussion between the investigator and the Sponsor. Rechallenge with a reduced dose of pexidartinib may result in a recurrence of increased serum transaminases, bilirubin, or ALP. Monitor liver tests weekly for the first month after rechallenge.

Table 7-1: Dose Modification Guidelines for Treatment-emergent Toxicities

Adverse Reaction	Severity	Pexidartinib Dosage Modifications
Increased ALT and/or AST	Greater than 3 to 5 times ULN	
 • Withhold and monitor liver tests weekly. • If AST and ALT are less than or equal to 3 times ULN within 4 weeks, resume at reduced dose. • If AST or ALT is not less than or equal to 3 times ULN in 4 weeks, permanently discontinue pexidartinib.

	Greater than 5 to 10 times ULN	
 Withhold and monitor liver tests twice weekly. If AST and ALT are less than or equal to 3 times ULN within 4 weeks, resume at reduced dose. If AST or ALT is not less than or equal to 3 times ULN in 4 weeks, permanently discontinue pexidartinib.
	Greater than 10 times ULN	
 Permanently discontinue pexidartinib. Monitor liver tests twice weekly until AST or ALT is less than or equal to 5 times ULN, then weekly until less than or equal to 3 times ULN.
Increased ALP and Gamma-glutamyl transpeptidase (GGT)	ALP greater than 2 times ULN with GGT greater than 2 times ULN	
 Permanently discontinue pexidartinib. Monitor liver tests twice weekly until ALP is less than or equal to 5 times ULN, then weekly until less than or equal to 2 times ULN.
Increased bilirubin	Total bilirubin greater than ULN to less than 2 times ULN or Direct bilirubin greater than ULN and less than 1.5 times ULN	
 Withhold and monitor liver tests twice weekly. If an alternate cause for increased bilirubin is confirmed and bilirubin is less than ULN within 4 weeks, resume at reduced dose. If bilirubin is not less than ULN in 4 weeks, permanently discontinue pexidartinib.
	Total bilirubin greater or equal to 2 times ULN or Direct bilirubin greater than 1.5 times ULN	
 Permanently discontinue pexidartinib. Monitor liver tests twice weekly until bilirubin is less than or equal to ULN.
Adverse reactions or other laboratory abnormalities	Severe or intolerable	
 Withhold until improvement or resolution. Resume at a reduced dose upon improvement or resolution.

Table 7-2: Additional Liver Evaluation

Evaluation	Comments
Increase frequency of testing liver chemistries to twice per week, including INR, and continue until liver chemistries have stabilized, and then reduce to weekly until liver chemistries return to normal or baseline.	Investigational treatment may be started after liver function tests recover to Grade 0 to 1 or baseline level, and in consultation with Medical Monitor.

Detailed history focusing on medications and substances used: alcohol, change in medication dosages, new medications added, attention to use of acetaminophen, OTC medication use, and recreational drug use. Check for change in diet or use of dietary supplements, with particular attention to dose and duration of any herbal product.	Suspect medications will be discontinued or substituted for if possible.
Detailed medical history and physical examination seeking new abnormalities.	Evaluate abnormalities found.
Full serological evaluation for hepatitis A, B, C, and E (IgG and IgM). Check for autoimmune hepatitis with serological laboratory studies.	If viral hepatitis or autoimmune hepatitis suggested, have patient evaluated by hepatologist.
Liver ultrasound performed to evaluate liver and biliary tree.	Evaluate any abnormalities found.
Check history for exposure to chemical agents.	Remove chemical exposure and have patient seen by hepatologist.
Obtain hepatology consult if liver function continues to rise beyond 14 days.	Contact Medical Monitor.
We request that cases be discussed with the Medical Monitor as defined in the protocol whenever investigational product is being held for liver function test abnormality.	

For suspected cases of cholestatic liver injury, eg, aminotransferase increase concurrent with hyperbilirubinemia, or liver biopsy suggesting cholestasis and/or ductopenia, patients will be followed to assess long-term outcome. Additional diagnostic and follow-up procedures might be implemented as appropriate to fully assess the event.

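### Section 7.5 gives two liver restart rules that disagree for patients enrolled above the Table 7-1 limits, and Table 7-1 makes no provision for Gilbert's Syndrome

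*Combined protocol and SAP*

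**What the plan says.** Section 7.5 of the protocol holds both rules.

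**Table 7-1, AST/ALT above 3 and up to 10 × ULN.** Withhold and monitor, then: "If AST and ALT are less than or equal to 3 times ULN within 4 weeks, resume at reduced dose". Otherwise: "If AST or ALT is not less than or equal to 3 times ULN in 4 weeks, permanently discontinue pexidartinib".

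**Table 7-1, lower bilirubin row** ("Total bilirubin greater than ULN to less than 2 times ULN or Direct bilirubin greater than ULN and less than 1.5 times ULN"). Withhold, then: "If an alternate cause for increased bilirubin is confirmed and bilirubin is less than ULN within 4 weeks, resume at reduced dose". The stop condition is: "If bilirubin is not less than ULN in 4 weeks, permanently discontinue pexidartinib".

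**Table 7-1, immediate permanent stop.** This applies to AST/ALT "Greater than 10 times ULN", to ALP and GGT both above 2 × ULN, and to "Total bilirubin greater or equal to 2 times ULN or Direct bilirubin greater than 1.5 times ULN".

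**Table 7-2, comment beside the row on more frequent liver testing.** "Investigational treatment may be started after liver function tests recover to Grade 0 to 1 or baseline level, and in consultation with Medical Monitor". The comment gives no recovery window and does not exclude the permanent-stop rows.

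**Interruption limit.** The Section 7.5 text before the tables, and Section 7.6, say that interruptions beyond 2 weeks lead in general to discontinuation. The exception is a patient with clinical benefit, after discussion with the Sponsor.

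**Entry limits.** Section 6.1, criterion 7b, admits AST/ALT below 5 × ULN with liver metastases, total bilirubin up to 1.5 × ULN, and total bilirubin up to 2.5 mg/dL in Gilbert's Syndrome.

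**The concern.** No sentence says which table governs restart. Table 7-1 works in absolute multiples of ULN. Table 7-2 also accepts a return to the patient's own baseline. For a patient enrolled above a Table 7-1 limit, the same recovered value can mean a permanent stop under one table and permitted restart under the other.

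The bilirubin row has a gap of its own. It does not say what to do when bilirubin normalises and no other cause is confirmed. Gilbert's patients are admitted because a raised total bilirubin is expected in them, but Table 7-1 counts that value towards hold and stop even if direct bilirubin is normal.

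At stake is rechallenge with a drug for which Section 7.5 warns that liver test abnormalities may recur. Section 3.3 reports severe cholestasis, one transplantation, and one death with cholestatic liver injury ongoing. In the other direction, a patient who is benefiting could lose the drug because a small rise has returned only to where it began.

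**Working it through.** This is a question of consistency between rules. No stated sample size, power or error rate depends on it, so there is no plan figure to reproduce. The check sets the thresholds side by side.

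**1. AST/ALT, raised baseline (liver metastases).** Take a baseline of 4.0 × ULN, allowed by 7b, and a 10% rise: 4.0 × 1.10 = 4.4 × ULN. This falls in the row above 3 to 5 × ULN, so the drug is held. Suppose the value is back at 4.0 at week 4.
- Table 7-1: 4.0 > 3.0, so stop permanently.
- Table 7-2: 4.0 equals baseline, so restart is permitted after Medical Monitor consultation.
- Fall below own baseline needed to resume under Table 7-1: (4.0 − 3.0)/4.0 = 25%.
- For a baseline b between 3 and 5 × ULN, the needed fall is (b − 3)/b. It runs from just above 0% to just under (5 − 3)/5 = 40%.

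**2. Total bilirubin, raised baseline, no Gilbert's.** Baselines above 1.0 and up to 1.5 × ULN are eligible. Table 7-1 requires a value below 1.0 × ULN, so a return to baseline never qualifies. The needed fall exceeds (1.3 − 1.0)/1.3 = 23.1% at a baseline of 1.3 × ULN, and (1.5 − 1.0)/1.5 = 33.3% at 1.5 × ULN.

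**3. Gilbert's at the 2.5 mg/dL entry cap.** The documents give no bilirubin ULN, so a range of 1.0 to 1.5 mg/dL is assumed.

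| Assumed ULN (mg/dL) | 2.5/ULN | 2 × ULN (mg/dL) | Table 7-1 row containing 2.5 | Fall needed to get below ULN: more than (2.5 − ULN)/2.5 |
|---|---|---|---|---|
| 1.0 | 2.50 | 2.0 | permanent stop | 60% |
| 1.2 | 2.08 | 2.4 | permanent stop | 52% |
| 1.25 | 2.00 | 2.5 | permanent stop | 50% |
| 1.3 | 1.92 | 2.6 | hold | 48% |
| 1.5 | 1.67 | 3.0 | hold | 40% |

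The crossover is 2.5/2 = 1.25 mg/dL. The reference to an alternate cause does not help these patients, because it is joined by *and* to bilirubin below ULN.

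**4. Lower bilirubin row, all outcomes at 4 weeks.**

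| | Below ULN | Not below ULN |
|---|---|---|
| Other cause confirmed | resume at reduced dose | stop permanently |
| No other cause confirmed | not addressed | stop permanently |

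**5. Time limits.** Table 7-1 allows 4 weeks. The general limit is 2 weeks, with the clinical-benefit exception. The Table 7-2 comment states none, but the general limit still applies. The week-4 example in step 1 is past 2 weeks, so it depends on that exception. Extension patients, who by definition have stable disease or better, could qualify for it.

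**The case against.** The strongest reply is that the two tables do different jobs. Table 7-1 is the dose-modification table. Table 7-2 concerns additional liver evaluation, and the sentence at issue is permissive, sits in a comments column and requires Medical Monitor consultation. Read naturally, it adds a condition and does not displace an instruction to stop permanently. The guidance is also limited to treatment-emergent, drug-related toxicity and yields to the treating physician's judgement. Rechallenge and liver holds go to the Medical Monitor, and Section 15.12 provides a hepatic Adjudication Committee.

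Much of this stands, and it rules out several stronger readings that a reader might infer:
- **That Table 7-2 reopens treatment after an immediate permanent stop.** A permissive comment does not readily override a mandatory stop. The missing exclusion is a drafting gap.
- **That the tables conflict for every patient.** The documents do not reproduce the CTCAE grade cut-offs, so no numerical conflict can be shown for recovery to Grade 0 to 1. It is shown only for raised baselines.
- **That restart under Table 7-2 is open-ended in time.** The general 2-week limit covers it.
- **That failure to confirm another cause of raised bilirubin leads to a permanent stop.** Table 7-1 attaches the stop only to bilirubin not below ULN at 4 weeks.
- **That a Gilbert's patient must be stopped at an unchanged baseline value.** Such a value need not be treated as a treatment-emergent toxicity.

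The reply does not remove the point. Section 7.5 refers to both tables for dose reductions, and Section 3.3 says the protocol's reductions and discontinuations should be followed. The added-condition reading is nowhere stated. The Medical Monitor limits divergence between sites but is handed both rules. That reading also leaves the Gilbert's gap and the unaddressed bilirubin outcome untouched.

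**Conclusion.** The inconsistency is in the text and is minor. Section 7.5 can give opposite answers for the same recovered value when a patient entered with AST/ALT above 3 and below 5 × ULN, or with total bilirubin above ULN. Three gaps accompany it: the 2-week and 4-week limits are not reconciled, bilirubin that normalises without another cause is not addressed, and Table 7-1 has no Gilbert's provision.

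The AST/ALT and non-Gilbert's figures rest only on the documents' limits and chosen example baselines. The Gilbert's figures rest on the assumed ULN range.

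Reach is small. Section 5.1 reports six patients enrolled and two ongoing at 30 June 2018, after which the sponsor discontinued the study and moved the remaining patients to the extension. A reader might infer that someone has been wrongly stopped or restarted. The documents do not say whether either extension patient had Gilbert's or a raised baseline, and they show no such event.

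**What to change.** Amend Section 7.5 as follows.

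1. State that Table 7-1 governs restart and permanent discontinuation. Replace the Table 7-2 comment with: *Treatment may be restarted only when the Table 7-1 restart limit is met and after consultation with the Medical Monitor; it may not be restarted where Table 7-1 requires permanent discontinuation.*
2. State that for liver holds the 4-week recovery window in Table 7-1 applies in place of the general 2-week limit, and cross-refer in Section 7.6.
3. State that bilirubin which normalises with no other cause confirmed does not permit restart.
4. For documented Gilbert's Syndrome, apply the direct-bilirubin limits for hold, restart and stop. In addition, hold and discuss with the Medical Monitor if total bilirubin rises above the patient's own baseline, so that total bilirubin still acts as a safeguard. Reporting of combined elevations under Section 13.1 stays on total bilirubin.

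The cost is a short amendment with written IRB/IEC approval and regulatory submission (Section 15.7), and renewed consent if the subject information changes (Section 15.8). No new test is needed, because total and direct bilirubin are already in the extension chemistry (Section 9.1.12).

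The clinical price is that patients without Gilbert's who entered with a raised baseline lose the option to restart at baseline and are held to the stricter rule. Given the liver risk described in Section 3.3 that choice is defensible, but the amendment should state it openly.
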